4.11 Materials needed to conduct the Clinical Ivestigation Plan

• Collagen Medical Device (MD-Tissue) 2 ml vials.

Such material will be sent by Guna S.p.a. to the pharmacy of the Investigational Site in a quantity suitable for the conduct of the Study."

4.12 Study group

• Group (Collagen Medical Device):

Experimental group will be treated with 2 ml volume ultrasound-guided infiltrations of:

• MD-Tissue (GUNA, Milan-Italy)

Composition per 2 ml: collagen 100 micrograms

Excipients: Ascorbic acid, Magnesium gluconate, Pyridoxine hydrochloride, Riboflavin, Thiamine hydrochloride, NaCl, Water for injection.

Subjects will be treated with 1 ultrasound-guided infiltration per week for 3 consecutive weeks.

4.13 Infiltrative Technique

The infiltrations will be performed in ultrasound mode by a radiologist experienced in musculoskeletal ultrasound techniques. The infiltration technique will be performed as follows:

The subject will be positioned in lateral decubitus with the GTPS-affected hip upwards.

A sterile field will be set up with disposable drapes and careful skin disinfection with 2% chlorhexidine and betadine.

Using a Convex probe, fitted with a sterile sheath, the greater trochanter, the bursa trochanteris and the tendons of the small and middle gluteal muscles will first be located, identifying the areas most affected by degenerative processes.

The infiltration will then be performed in complete asepsis, using a 20G disposable spinal needle.

MD-Tissue *Collagen Medical Device* will be infiltrated into the trochanteric bursa and at the level of the tendons of the gluteus minimus and gluteus medius, particularly at the level of the most degenerated insertional areas.

4.14 Criteria for effectiveness

4.14.1 End Point Primario

The objective of this study is to evaluate the efficacy of the experimental treatment in terms of reduction of referred pain in the peritrochanteric area, of the hip affected by GTPS.

The primary endpoint will be assessed at 10 weeks and will include:

• Evaluation of the NRS score at time 10 weeks compared to time T0. It can be considered clinically significant if at least 50% of the treated subjects show a reduction of at least 3 points on the NRS scale.

4.14.2 Secondary End Points

- Evaluation of the NRS score at time weeks 6 and weeks 24 compared to time day 0.
- Evaluation of mHHS score at time weeks 6, weeks 10, and weeks 24 compared to time day 0.

_

- Clinical evaluation of abduction stenia at time weeks 6, weeks 10, and weeks 24 compared to time day 0.
 - [the stenia will be assessed, with the subject standing on the healthy limb, through measurements of the abduction force of the GTPS-affected hip, using a dynamometer]
- Evidence of resolution or decrease in inflammatory and degenerative signs of the peritrochanteric region of the GTPS-affected hip on MRI investigation at weeks 24 compared to day 0.
- Assessment of analgesic drug unit consumption based on clinical diary at day 0, week 1, week 2, weeks 6, weeks 10 and weeks 24.
 - [Celecoxib 200mg cpr 1 tablet/day will be used as a pain killer, in case of onset/recurrence of pain; if the subject is hypertensive or intolerant Paracetamol 1000mg cpr 2 tablets/day].
- Evaluation of the fraction of subjects who drop out of the Clinical Investigation Plan early in relation to Adverse Events (AE/SAE/SUSAR).

4.15 Data collection

All data resulting from the Clinical Investigation will be entered, within seven days of their collection, into the electronic Data Collection Form (e-CRF) "Pheedit Dedagroup" provided by the

Sponsor. Radiological data will be collected and stored digitally on the PACS system. Data entry procedures will be performed by the Data Manager.

4.16 Early abandonment of the Clinical Study

I Subjects may leave the Clinical study for the following reasons:

- a. at their own request (even without justification);
- b. at the investigator's discretion;
- c. if they experience an Adverse Event.

The reason for abandonment will be stated in the e-CRF.

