The occurrence of Adverse Events will be assessed at each visit. All Adverse Events (AEs), Serious Adverse Events (SAEs) and Suspected Serious and Unexpected Adverse Reactions (SUSARs) occurring between the date of signing the Informed Consent and the end of the Clinical Investigation will be recorded and reported.

All data collected will have to be entered by the Principal Investigator or a Co-Investigator identified by the Principal Investigator into the Electronic Data Collection Sheet provided by Guna S.p.a.

In particular, it is planned to obtain a data collection that is schematically described in the following table (Tab. 1), in which the entries to be made at each visit are shown:

PROCEDURE	VISIT	VISIT	VISIT	VISIT	VISIT	VISIT
SPERIMENTALI						
	Т 0	T 1	T 2	T 6/FU	T10/FU	T24/FU
		WEEKS	WEEKS	WEEKS	WEEKS	WEEKS
	enrolment	Visit	Visit	Control visit	Control visit	End of Clinical
	1°	2°	3°			Investigation
	infiltration	infiltration	infiltation			
Clinical diagnosis of	X					
GTPS						
Evaluation of Selection	X					
Criteria						
Signature of informed	X					
consent						
Signature of consent to	X					
personal data						

processing						
Collection of socio-	X					
demographic data						
Medical history	X					
collection						
NRS Evaluation	X			X	X	X
Assessment of pain on	X			X	X	X
palpation according to						
NRS						
mHHS assessment	X			X	X	X
Assessment of stenia in	X			X	X	X
abduction						
Evaluation of phlogistic	X					X
and degenerative signs						
on MRI						
Infiltrative Treatment	X	X	X			
Evaluation of clinical	X	X	X	X	X	X
diary						
Adverse Event	X	X	X	X	X	X
Evaluation (AE/SAE)						

Tab.1 Data collection during the Clinical Investigation Plan

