5. STATISTICS

5.1 Dimensione del campione

This is a one-sample study. It is assumed that the proportion of successes (patients who have a reduction of at least 3 points on the NRS scale) in the absence of treatment cannot exceed 25%, (H0) while, in section 4.14.1, a success rate of at least 50% (HA) in treated subjects was assumed to be clinically significant.

Under these assumptions, an exact one-tailed binomial test applied to a sample of 49 subjects achieves a power of 95.7% in discriminating the 25% difference between the proportion predicted by HA and that predicted by H0, at a significance level of 0.025 (the significance level calculated by simulation is instead 0.023, thus below the target for the one-tailed test).

There is no inflation of the sample size determined by possible dropouts, as every such subject will automatically be considered a failure.

Incidentally, it is also pointed out that by the time the 19th success is reached, the null hypothesis can already be rejected, as 19 successes out of 49 would represent a proportion of 38.776%, which has an exact 95% binomial confidence interval ranging from 25.197% to 53.761%, so that the maximum proportion of 25% predicted by H0 would be below the lower margin of the confidence interval.

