Adverse Events that have not yet resolved at the end of the study will be followed up by the Investigator; each subject who has experienced an Adverse Event will be contacted at least once a month after the conclusion of the study for as many months as deemed appropriate.

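### Section 4.16 does not separate stopping the infiltrations from leaving the study, so secondary outcomes and new adverse events can go uncollected in subjects who tolerate the device poorly

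*Combined protocol and SAP*

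**What the plan says.** Section 4.16 opens with "Subjects may leave the Clinical study for the following reasons" and lists three grounds: the subject's own request, "at the investigator's discretion", and "if they experience an Adverse Event". The second has no criteria. The third has no threshold of severity or relatedness, and section 5.6 grades adverse events down to mild ones. The only item required on leaving is the reason: "The reason for abandonment will be stated in the e-CRF". No section describes stopping the infiltrations while staying in follow-up, an exit visit, or later assessments for leavers.

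Section 5.1 sets the primary-analysis rule: "There is no inflation of the sample size determined by possible dropouts, as every such subject will automatically be considered a failure". Section 5.2.3 names repeated-measures ANOVA or Friedman tests for NRS, mHHS, abduction strength and analgesic use, and a paired t-test or Wilcoxon test for MRI. It gives no rule for missing values.

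On safety, section 4.10.2 says "The occurrence of Adverse Events will be assessed at each visit" and that all events from consent to the end of the investigation are recorded. Section 5.6 requires every event to be monitored and adds: "Adverse Events that have not yet resolved at the end of the study will be followed up by the Investigator". It also provides at least monthly contact, after the study has concluded, with each subject who had an event.

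**The concern.** The infiltrations are given at day 0, week 1 and week 2 (sections 4.10.1 and 4.12). The remaining 24 − 2 = 22 weeks are follow-up only. After week 2 there is no infiltration left to stop, so an exit on the second or third ground costs data and changes nothing in the study treatment. Neither ground requires the subject to refuse further assessment, so the loss is avoidable.

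The study is single-arm, with every subject on the device, so the investigator using this discretion knows the treatment and can see how the subject is doing. If those who react badly, or who are removed, have no later measurements, the secondary results describe mainly those who did well. Adverse events could also be under-recorded in the subjects who have already reacted.

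**Working it through.** **The plan's own figure.** Inputs from section 5.1: N = 49, H0 25%, HA 50%, one-tailed exact binomial test, nominal level 0.025, rejection at 19 or more successes.

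- Level: P(X ≥ 19) for Binomial(49, 0.25) = 0.0231. The plan states 0.023.
- Power: P(X ≥ 19) for Binomial(49, 0.50) = 0.9573. The plan states 95.7%.
- A cut-off of 18 would give a level of 0.0456, so 19 is the right cut-off.

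The stated figures are reproduced.

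**Primary test when leavers count as failures.** Let d be the fraction leaving before week 10. The documents give no value, so d is an assumption. If leaving is independent of response, the counted success rate is 0.50 × (1 − d) under HA and 0.25 × (1 − d) under H0, with the cut-off still 19 of 49.

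| d | Power | Level |
|---|---|---|
| 0% | 95.7% | 0.0231 |
| 5% | 91.5% | 0.0136 |
| 10% | 84.6% | 0.0075 |
| 20% | 62.2% | 0.0019 |

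The level falls as d rises, so the failure rule is conservative.

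**What measuring the leavers would recover.** Let q be the leavers' true success rate. The counted rate becomes 0.50 × (1 − d) + q × d.

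| d | q = 0% | q = 25% | q = 50% |
|---|---|---|---|
| 10% | 0.45 → 84.6% | 0.475 → 91.5% | 0.50 → 95.7% |
| 20% | 0.40 → 62.2% | 0.45 → 84.6% | 0.50 → 95.7% |

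If leavers would not have responded, measuring them recovers no power, because an imputed failure and an observed failure are the same. The avoidable cost appears only as q rises above zero.

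**Secondary outcomes.** Expected numbers with data are 49 × 0.90 = 44.1 at 10% leaving and 49 × 0.80 = 39.2 at 20%. Standard repeated-measures ANOVA and Friedman tests need a complete row per subject. A subject who leaves after week 6 would therefore usually lose the week 6 value from the test as well.

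To illustrate the selection, assume completers average a −3.0 point NRS change:

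- 10% leave with no change: 0.9 × (−3.0) + 0.1 × 0 = −2.7 over all treated, against −3.0 as analysed.
- 10% leave with an average change of −1.5: 0.9 × (−3.0) + 0.1 × (−1.5) = −2.85.
- 20% leave with no change: 0.8 × (−3.0) + 0.2 × 0 = −2.4.

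The gap runs from 0.15 to 0.6 points across these assumed cases. It would be zero if leavers changed as completers did.

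**Safety text side by side.** Section 4.10.2 promises all events to the end of the investigation, but its means of collection is the visit, and no visit is provided for a leaver. The monitoring duty in section 5.6 covers the event that prompted leaving, and its monthly contact starts after the study ends. Neither section says how a new event between leaving and week 24 would be found.

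**The case against.** The strongest reply is that the main analysis is already safe. All 49 subjects stay in the primary test, the type I error cannot rise, and treating intolerance as failure is a recognised conservative choice against a fixed 25%. Replacing it with observed values would be a change of estimand. It could favour the device if a subject stopped infiltrations and then improved on another treatment. This stands, and the failure rule should remain.

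Second, section 4.16 is permissive. A reader might infer that an adverse event obliges the site to close the subject out. The wording allows leaving and does not require it, so loss is possible and not certain.

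Third, a reader might infer that all safety data after leaving are lost. The documents do not support that. Sections 4.10.2 and 5.6 together cover the event that led to leaving, and the monthly contact does not exclude early leavers. What remains is the narrower gap for new events before week 24.

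Fourth, leaving because of adverse events is itself a secondary endpoint with a 95% confidence interval (sections 4.14.2 and 5.2.3), so this part of the selection would be visible. That shows how many left. It does not supply their missing outcomes, and it does not count removals at the investigator's discretion for other reasons.

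**Conclusion.** The point holds as a gap in data collection. Section 4.16 merges stopping treatment with leaving the study and provides for no assessments afterwards. The main consequence is that NRS at weeks 6 and 24, mHHS, abduction strength, MRI and analgesic use can be selectively missing in subjects who tolerated the device poorly. New adverse events in leavers also lack a stated route to the record.

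For the primary test the effect is limited to power and depends on an unknown. At an assumed 10% leaving, power is 84.6% as planned, and measuring leavers would give between 84.6% and 95.7% as their true success rate runs from 0% to 50%. A reader might take a drop from 95.7% to 90.8% with 3 leavers, or to 85.4% with 5, as the cost of section 4.16. Those figures hold only if leavers would have responded at 50%. They cannot be combined with the illustration of leavers who do not change, because in that case the primary test loses nothing that follow-up could recover.

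The dropout rates and the NRS changes are assumptions. The change should be made, but the gap does not invalidate the primary analysis.

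**What to change.** Limit the change to data collection and leave the clinical grounds for stopping infiltrations as they are.

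- **Section 4.16:** add that subjects who stop infiltrations, or who leave on the second or third ground, are asked to continue the week 6, 10 and 24 assessments already scheduled, unless they withdraw consent to follow-up. If they will not attend, collect NRS and adverse events by telephone.
- **Section 5.2.3:** use these observed data in the secondary and safety analyses.
- **Sections 5.1 and 5.2.2:** keep dropout as failure for the primary test, and report the response based on observed week-10 NRS as a sensitivity analysis.
- **Sections 4.10.2, 4.16 and 5.6:** reconcile them so that adverse-event contact for leavers who still consent runs from the time of leaving to week 24.

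The cost is a few telephone contacts or attendances at visits already in the schedule, plus an amendment that needs ethics committee approval under section 5.4. It should be settled before subjects leave, because assessments not made at the time cannot be recovered.

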5. STATISTICS

5.1 Dimensione del campione

This is a one-sample study. It is assumed that the proportion of successes (patients who have a reduction of at least 3 points on the NRS scale) in the absence of treatment cannot exceed 25%, (H0) while, in section 4.14.1, a success rate of at least 50% (HA) in treated subjects was assumed to be clinically significant.

Under these assumptions, an exact one-tailed binomial test applied to a sample of 49 subjects achieves a power of 95.7% in discriminating the 25% difference between the proportion predicted by HA and that predicted by H0, at a significance level of 0.025 (the significance level calculated by simulation is instead 0.023, thus below the target for the one-tailed test).

There is no inflation of the sample size determined by possible dropouts, as every such subject will automatically be considered a failure.

Incidentally, it is also pointed out that by the time the 19th success is reached, the null hypothesis can already be rejected, as 19 successes out of 49 would represent a proportion of 38.776%, which has an exact 95% binomial confidence interval ranging from 25.197% to 53.761%, so that the maximum proportion of 25% predicted by H0 would be below the lower margin of the confidence interval.

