4.7 Inclusion Criteria

- male and female subjects aged between 18 and 70 years;
- subjects with lateral palpatory pain that has appeared for at least 1 month;
- subjects with pain symptoms of the hip assessed according to the Numerical rating scale (NRS) ≥ a 5;
- subjects who are able to cooperate with the assessments in the investigation plan;
- Subjects able to understand and sign informed consent.
- (NB. Subjects with bilateral hip pain symptoms will be included for the more symptomatic side and treated monolaterally).

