4.10.2 Visit Paln

TO BASAL: Enrolment

In the course of daily clinical activity, investigators participating in the Clinical Ivestigation Plan will select subjects with GTPS. The Principal Investigator will be responsible for the correct clinical diagnosis, also making use of the instrumental examinations provided for in the Investigation Plan. Subjects meeting the inclusion and exclusion criteria will thus be identified. After having thoroughly explained the aims, purposes and procedures foreseen by the Investigation Plan, the subject will be proposed to participate in the Investigation itself. Finally, the selected subject will be asked to read the information form and to date and sign the Informed Consent and Consent to the Processing of Personal Data form.

Female subjects will have to provide evidence of a negative pregnancy test in order to be enrolled.

We will then proceed with the objective examination and the collection of the information required by the electronic Data Collection Form appropriately prepared.

This will be followed by:

- pain assessment using the NRS scale;
- assessment of pain using the Modified Harris Hip Score (mHHS) scale;
- clinical assessment of pain on palpation of the trochanter using the NRS scale;
- clinical assessment of stenia in abduction of the lower limb with the dynamometer;
- clinical assessment of phlogistic-degenerative signs by MRI of the peritrochanteric region;

The first infiltration will then be performed by means of ultrasound.

Previous or ongoing pharmacological treatments of any kind will be documented.

In order to monitor the consumption of analgesic (celecoxib 200mg / paracetamol 1000 mg) used during the investigation in the event of the onset of pain, a clinical diary will be given to the subject in which to indicate the day and the dose of drug used.

The enrolled subject will be assigned an identification code of a complex type formed by the progressive enrolment number followed by an alphanumeric code generated by GUNA S.p.a. through *Random Sequence Generator* (www.random.org.)

TO BASAL: Enrolment

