5.2.2 Primary Endpoint

The primary endpoint will be assessed with one-tailed exact binomial tests, as described in section.

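### Does the unsourced 25% null rate, with rejection from 19 of 49, call for a different null or cut-off for the primary test?

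*Combined protocol and SAP*

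**What the plan says.** Section 5.1 describes a one-sample study with 49 subjects. A success is a fall of at least 3 NRS points; section 4.14.1 places the comparison at week 10 against T0. The null is that the success proportion "in the absence of treatment cannot exceed 25%, (H0", and the alternative is 50%. The test is exact binomial, one-tailed at 0.025, with a stated attained level of 0.023 and a stated power of 95.7%. Dropouts count as failures. As an aside, the section notes that "by the time the 19th success is reached, the null hypothesis can already be rejected", because "the maximum proportion of 25% predicted by H0 would be below the lower margin of the confidence interval".

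Section 5.2.2 adds only that "The primary endpoint will be assessed with one-tailed exact binomial tests" and points back to a section whose number is missing. Section 5.1 is the only one that fits.

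Section 4.14.1 carries a second criterion: "It can be considered clinically significant if at least 50% of the treated subjects show a reduction of at least 3 points".

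Three other provisions bear on the background response:
- Analgesics are available: section 4.10.2 provides a diary for celecoxib or paracetamol "used during the investigation in the event of the onset of pain", and section 4.14.2 says that celecoxib "will be used as a pain killer, in case of onset/recurrence of pain", with paracetamol as the alternative.
- Section 4.7 admits "subjects with lateral palpatory pain that has appeared for at least 1 month" with an NRS of 5 or more.
- Section 4.3 and the synopsis call the study a single-centre, one-sample pilot.

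**The concern.** Without a control arm, the test result rests entirely on the 25%. The plan words it as the rate without treatment and cites nothing. Trial subjects are not simply untreated apart from the device. They can take analgesics, they undergo three ultrasound-guided injections, and they are selected for high pain, in some cases of only a month's duration. Regression to the mean, natural recovery, analgesia and the procedure itself could each produce 3-point falls.

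The margin is thin. At 19 of 49 the lower exact limit is 25.197%, which clears the null by 0.2 points. If the background is somewhat above 25%, the one-sided error is well above its nominal level, while section 5.10 intends the final report to reach dependable conclusions on efficacy. With 19 to 24 responders the test would be positive and the 50% mark missed, and the plan does not say which of the two supports the efficacy statement.

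**Working it through.** **Inputs.** From section 5.1: n = 49, null p0 = 0.25, alternative p1 = 0.50, one-sided level 0.025. From section 4.14.1: 50% of 49 is 24.5, so the mark is met from 25 responders. Background rates other than 25%, and all dropout rates, are assumptions.

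**Formula.** P(X ≥ r | p) = Σ over k = r to 49 of C(49, k) p^k (1 − p)^(49 − k).

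**1. The plan's own figures.** At p = 0.25, r = 18 gives 0.0456 and r = 19 gives 0.0231, so 19 is the smallest count that rejects at 0.025. Power is P(X ≥ 19 | 0.50) = 0.9573. The exact 95% interval for 19/49 is 25.197% to 53.761%. All three agree with section 5.1.

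**2. An ineffective device at other background rates.**

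| Background (net of dropouts) | P(X ≥ 19) | P(X ≥ 25) |
|---|---|---|
| 25% | 2.3% | 0.01% |
| 27.5% | 5.7% | 0.04% |
| 30% | 11.9% | 0.17% |
| 32.5% | 21.4% | 0.55% |
| 35% | 33.9% | 1.5% |

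The test alone is sensitive to the null rate. The 50% mark is not, over this range: even at 35% it is reached less often than the 2.3% accepted at 25%. Almost all the excess lies at 19 to 24 responders (0.1194 − 0.0017 = 0.1177 at 30%; 0.3386 − 0.0154 = 0.3232 at 35%), where section 4.14.1 already withholds the label of clinical significance.

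**3. Dropouts as failures.** If a rate p applies to completers and a fraction d drops out, the test sees p(1 − d).

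| d | Completers 30% | Completers 35% |
|---|---|---|
| 5% | 0.285: P(X ≥ 19) = 7.8% | 0.3325: 24.9% |
| 10% | 0.270: 4.9% | 0.315: 17.2% |
| 15% | 0.255: 2.8% | 0.2975: 11.2% |

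With d = 10%, a completer rate of 28% gives 0.28 × 0.90 = 0.252 and an error of 2.5%. The dropout rule offsets part of any upward pressure, so the range of 11.9% to 33.9% holds only if 30% to 35% is already net of dropouts.

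**4. What a higher null would cost at n = 49.**

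| Null | Cut-off | Attained level | Power at 50% |
|---|---|---|---|
| 25% (plan) | 19 | 0.0231 | 95.7% |
| 30% | 22 | 0.0195 | 80.4% |
| 35% | 25 | 0.0154 | 50.0% |

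The loss is 95.7 − 80.4 = 15.3 points or 95.7 − 50.0 = 45.7 points, in exchange for a null rate that has no more source in the documents than 25% has.

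**5. Direction of the analgesic effect.** Section 5.1 contrasts subjects without treatment with treated subjects, so treatment most naturally means the device, and on-demand analgesic can be present on both sides of that contrast. Ongoing drugs are documented at T0 and the diary is reviewed at every visit. Whether use rises or falls between T0 and week 10 cannot be known in advance, so the documents do not fix the direction in which it shifts a change score.

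**The case for a change.** The strongest case for acting is that a small excess is enough. At 27.5% the error is already 5.7%, more than double 2.3%. Moving from 25% to 30% takes 0.05 × 49 = 2.45 extra responders. The 50% mark would protect the conclusion if it bound, but section 5.2.2 does not make it part of the test. The zone of 19 to 24 responders is not remote either: at a true 50% its probability is 0.9573 − 0.5000 = 45.7%. Dropouts offset only part of the inflation, and stating a source before the data are seen would cost a few lines of text.

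The sensitivity is real, and so is the missing source; a report that gave 20 of 49 as proof of efficacy without comment would claim too much. But nothing in the documents places the background above 25%. The figure of 2.45 responders is worked backwards from 30% and is not evidence for it. Any fixed null in an uncontrolled study would face a similar table, and the plan states openly that it is a one-sample pilot. Labelling 19 to 24 responders as above 25% but short of the clinical mark only says what sections 5.1 and 4.14.1 together already say. Given the count out of 49, any reader can form the exact interval and set it against a preferred background rate.

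**Conclusion.** No change to the plan follows. The calculation in section 5.1 is correct, and the 2.3% error holds under the null it states. The error rises to 11.9% to 33.9% only if the background rate, net of dropouts, is 30% to 35%, which is an assumption. Over that range the mark in section 4.14.1 would be met by chance in 0.17% to 1.5% of trials.

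The absent source for 25% is missing detail that the authors of the report can supply or acknowledge. The two criteria answer different questions, one about evidence against 25% and the other about clinical relevance, and a sensible analyst reports both with the exact interval. Moving the cut-off would give up 15.3 to 45.7 points of power at the plan's own alternative, with no documented reason to prefer the new null. This conclusion assumes that a result of 19 to 24 responders is read against section 4.14.1 as well as the test. Documented evidence of a background rate well above 25% under trial conditions would reopen the question.

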1. SYNOPSIS

TITLE	Evaluation of the efficacy of the use of a Type I Collagen medical device						
	(MD-Tissue Collagen Medical Device) in the infiltrative treatment of						
	Great Trochanter Pain Syndrome. "MEDANTRO PILOT STUDY".						
STUDY DESCRIPTION	Single-centre pilot clinical investigation based on a one-samp						
	design.						
	Variables will be assessed at 6 different times: at baseline (day 0),						
	after week 1, weeks 2, weeks 6, weeks 10 and after weeks 24, i.e. 6						
	months after the start of the Clinical Investigation.						
OBJECTIVES	The objective of this study is to evaluate the efficacy of the						
	experimental treatment in terms of reduction of referred pain in						
	peritrochanteric area of the hip affected by GTPS.						
PRIMARY ENDPOINT	The primary endpoint will be assessed at week 10 and will include:						
	Assessment of the NRS score at weeks 10 compared to time						
	day 0. It can be considered clinically significant if at least 50%						
	of the treated subjects show a reduction of at least 3 points on						
	the NRS scale.						
POPULATION	A total of 49 subjects with GTPS will be enrolled.						
SELECTION CRITERIA	Inclusion criteria						
	 male and female subjects aged between 18 and 70 years; 						
	• subjects with lateral palpatory pain that has appeared for at						
	least 1 month;						
	• subjects with pain symptoms of the hip assessed according to						
	the Numerical rating scale (NRS) ≥ a 5;						
	• subjects who are able to cooperate with the assessments in						
	the investigation plan;						
	 subjects able to understand and sign the informed consent. 						
	Exclusion criteria						
	• subjects suffering from true coxalgia (with positive FADDIR)						
	 subjects suffering from ESHS (External Snap Hip Syndrome); 						
	• subjects who have already undergone candidate hip						
	replacement surgery;						
	subjects with radiological and clinical evidence of detachment						
	of the tendons of the lesser and/or middle gluteus with an						

	indication for surgical repair;				
	• subjects with evidence of radiographically documented				
	tendon calcifications;				
	• subjects with a degree of coxarthrosis of the hip that is a				
	candidate for treatment according to the Tonnis>1				
	classification				
	subjects who have taken fluoroquinolones within 30 days				
	prior to enrolment				
	subjects who have undergone treatment with hyaluronic acid				

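### Does naming 50% as the alternative turn a rejection of 25%, possible from 19 of 49, into a claim that half of patients respond?

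*Combined protocol and SAP*

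**What the plan says.** Section 5.1 (sample size) takes the success proportion, meaning a fall of at least 3 NRS points, which "in the absence of treatment cannot exceed 25%, (H0") as the null. For the alternative it says that "a success rate of at least 50% (HA) in treated subjects was assumed to be clinically significant", and it refers to section 4.14.1 for that judgement. With 49 subjects and a one-tailed exact binomial test at 0.025 it gives a power of 95.7% and an attained level of 0.023. It adds that "by the time the 19th success is reached, the null hypothesis can already be rejected, as 19 successes out of 49" is 38.776%, with an exact 95% interval of 25.197% to 53.761%, so that "the maximum proportion of 25% predicted by H0 would be below the lower margin of the confidence interval". On dropouts it says that "every such subject will automatically be considered a failure".

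Section 4.14.1 says the week-10 result can be "considered clinically significant if at least 50% of the treated subjects show a reduction of at least 3 points on the NRS scale", and the synopsis agrees. Section 5.2.2 says that "The primary endpoint will be assessed with one-tailed exact binomial tests" and leaves its section reference blank. Only 5.1 describes such a test, so the reference can only be to 5.1.

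**The concern.** Rejecting a null of 25% or less supports a rate above 25% and nothing more. Yet the only alternative that 5.1 names is 50% or more, and it attaches clinical significance to that rate. Read literally, true rates between 25% and 50% belong to neither hypothesis, and a reader could take rejection as support for the one named alternative.

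Section 4.14.1 and the synopsis speak of what treated subjects show, so 50% can also be read as a bar on the observed proportion. A result such as 20 of 49 would then clear the test and miss the clinical bar. No section says in so many words how that should be reported. Section 5.10 promises a final report with conclusions on clinical efficacy, so the wording of that conclusion is at stake.

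**Working it through.** **Inputs.** From 5.1: n = 49, null rate 0.25, design rate 0.50, one-sided level 0.025, rejection from 19 successes, dropouts counted as failures. From 4.14.1: clinical benchmark of 50%. I assume that all 49 subjects form the denominator, as the dropout rule implies. True rates of 35%, 40% and 45% are illustrative and do not come from the plan.

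**Step 1: reproduce the plan's figures.** The formula is P(X ≥ r | p) = Σ C(49,k) p^k (1−p)^(49−k), summed over k = r to 49.

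- P(X ≥ 18 | 0.25) = 0.0456, which exceeds 0.025. P(X ≥ 19 | 0.25) = 0.0231, which does not. The critical count is therefore 19, as stated.
- P(X ≥ 19 | 0.50) = 0.9573, the stated 95.7%.
- 19/49 = 38.776%. The Clopper-Pearson limits are the 0.025 quantile of Beta(19, 31) and the 0.975 quantile of Beta(20, 30). They are 25.197% and 53.761%, as stated.

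**Step 2: find where the two thresholds part.** Half of 49 is 24.5, so an observed rate of at least 50% needs 25 successes (51.0%). Results of 19 to 24 (38.8% to 49.0%) reject the null and fall short of 50%. The last column is P(X ≥ 19) − P(X ≥ 25), taken before rounding.

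| True rate | P(X ≥ 19) | P(X ≥ 25) | P(19 to 24) |
|---|---|---|---|
| 35% | 0.3386 | 0.0154 | 0.3232 |
| 40% | 0.6223 | 0.0776 | 0.5447 |
| 45% | 0.8460 | 0.2403 | 0.6058 |
| 50% | 0.9573 | 0.5000 | 0.4573 |

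At the design rate, 0.4573/0.9573 = 47.8% of rejections fall in this zone. The rejections at 35%, 40% and 45% are not errors: the true rate exceeds 25% in each case, so the null is false and the test is right to reject it.

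**Step 3: see what the plan says about a result in that zone.** At 19 successes the exact interval is 25.2% to 53.8%; at 24 it is 34.4% to 63.7%. Both exclude 25% and include 50%. Section 5.1 uses the interval only to exclude 25%, which is all it supports. Section 4.14.1 compares the proportion with 50%. Applied together, they describe 19 to 24 successes as statistically above 25% and below the clinical benchmark. The thresholds are nested, since 25 or more successes always reject 25%, so no result meets the benchmark and fails the test.

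**Step 4: ask what a change would gain.**

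- Restating the alternative as a rate above 25% leaves the critical count at 19, the level at 0.0231 and the power at 95.7%. No result changes.
- Defining success as 19 of 49 and calling 50% a power assumption would set 38.8% as the bar and demote a criterion that the sponsor declared in two places. That is a debatable substantive choice, not a correction.
- Adding operating characteristics for an observed 50% rule (met with probability 50.0% at a true rate of 50%) helps only if the sponsor intends it as a formal rule. Section 5.2.2 names only the binomial test.

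**The case for a change.** The strongest case for acting is that the zone where the readings differ is not rare. Even if the design assumption holds exactly, the trial lands there with probability 45.7%. Two authors could then stress opposite conclusions, one citing the rejected null and the other the missed 50%. Fixing the meaning before the data are seen costs a sentence and no patients.

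Part of this stands. The plan does not spell out how rejection of 25% relates to the 50% benchmark, and one sentence would settle it. The stronger claim, that the plan equates rejection with a rate of at least 50%, does not stand. Section 5.1 states only that the null can be rejected, gives the full interval, and compares its lower limit with 25%. The gap between 25% and 50% belongs to any design that pairs a null rate with a target rate, where the target is the point at which power is calculated. The three sections already agree on the 50% and on its clinical meaning, so there is no conflict of wording between them.

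**Conclusion.** No change to the plan follows. The test, sample size, level, critical count and power are correct and reproduce exactly, and calling 50% the alternative follows ordinary single-arm practice. What is missing is a detail that an analyst can fill sensibly: report the observed proportion of 49 with its exact 95% interval, state the result against 25%, and state separately whether 50% was reached. For 19 to 24 successes that gives a sound conclusion, above 25% but short of the benchmark. It affects how the result is described, not the type I error or the power, and its weight is limited in a one-arm pilot.

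This rests on three assumptions: all 49 subjects are the denominator, the blank reference in 5.2.2 points to 5.1, and the report does not present rejection of 25% as proof of 50%. Nothing in the documents invites that last reading.
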